There has been much speculation for decades regarding the cause of Alzheimer's Disease. Two of the many theories are the focus of our research study. The first theory posits that toxic brain concentrations of ammonia play a role in the AD pathophysiology (Seiler, 1993). There have, however, been no published trials of using ammonia lowering medications for the treatment of AD. The second and more recent theory proposes that there is a symbiotic relationship between gut microbiota and brain homeostasis and that this relationship is disrupted in patients with AD, possibly due to an imbalance in the ratio of pro-inflammatory / anti-inflammatory gut microbiota (De-Paula et al, 2018, Cattaneo et al, 2017).

Background

Rifaximin is a virtually non-absorbed antibiotic with the unique properties of lowering blood ammonia levels and altering gut flora. We hypothesize that Rifaximin will improve cognition and function in AD patients by lowering blood ammonia and / or lowering circulatory pro-inflammatory cytokines secreted by harmful gut bacteria.

We will be measuring blood ammonia levels and pro-inflammatory and anti-inflammatory compounds in the blood and analyzing gut microbiota in patients with AD before and after 3 months of Rifaximin therapy. If patients exhibit measurable improvement in cognition and function, we will analyze our data to see if their improvement correlates with a lower blood ammonia level and / or a shift towards anti-inflammatory species in the gut and a similar shift in the blood cytokine panel to favoring anti-inflammatory compounds.

Evidence supporting our hypothesis for this study is presented below.

Ammonia Neurotoxicity

Ammonia is a substrate as well as a product of 16 different enzymatic reactions in the brain. In the healthy brain, ammonia homeostasis is maintained by its combining with glutamate to form non-toxic glutamine via the glutamine synthetase pathway. In the disease state, high brain ammonia levels adversely affect membrane potential, mitochondrial function, astrocyte morphology, energy metabolism, mRNA and protein expression, brain pH, calcium signaling and other cellular functions in the brain (Bosoi et al, 2009).

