The brain also receives exogenous ammonia, of which the gut is a major source. Fecal bacteria produce ammonia by fermenting protein. The aging colon contains a greater percentage of protein fermenting bacteria than is seen in the colon of younger patients (Woodmansey, 2007, Andrieux et al, 2002). The aging colon also has a longer fecal dwell time than that of younger patients, allowing higher levels of ammonia to build up before fecal evacuation (Woodmansey, 2007, Andrieux et al, 2002). Gut ammonia is absorbed into the portal venous system and detoxified in the liver to form uric acid, which is then excreted in the kidneys. The uric acid cycle of the aging liver is less efficient at detoxifying ammonia (Marchesini, 1990) allowing higher levels of ammonia to reach the systemic circulation. One study reported significantly elevated post prandial blood ammonia levels in AD patients when compared with age-matched controls (Fisman et al, 1985).

The blood brain barrier plays an important role in regulating brain ammonia metabolism (Hawkins, 2009). 20-50% of blood ammonia passes the blood brain barrier and is converted into glutamine. Glutamine and glutamate are pumped from the extracellular fluid into the endothelial cells, where glutamine is partially metabolized to ammonia and glutamate. Glutamine and ammonia then diffuse into the blood.

Breakdown of the blood brain barrier in the aging patient begins in the hippocampus, the area critical for learning and memory, and this may contribute to cognitive decline (Erdo et al, 2017). Gadolinium enhanced Brain MRI has shown that the blood brain barrier is more permeable in the aging patient when compared with younger patients (Montagne et al 2015). The blood brain barrier in the AD patient is also more permeable than that of non-cognitively-impaired age matched controls (Montagne et al, 2015). High concentrations of Gadolinium are first seen in the hippocampus, the site responsible for memory and learning, both of which are clinically impaired in AD patients.

One theory is that the blood brain barrier allows greater amounts of ammonia into the AD brain, triggering or worsening pre-existent changes.

This study aims to lower blood and brain ammonia levels in AD patients by targeting the colon. This will be accomplished by administering a virtually non-systemically absorbed antibiotic, rifaximin, which is FDA approved for hepatic encephalopathy. Rifaximin

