This is an open label pilot study in which we will consent up to 25 subjects in order to treat 10 eligible subjects with probable mild to moderate AD. The study is single site and non-randomized. The subjects will be given rifaximin 550 mg orally twice daily for 3 months after evaluation to ensure they have no contraindications. Subjects at risk for drug interactions or tolerability issues may be started and/or maintained on a lower dose of 550 mg once a day. Individuals on concomitant drugs which are contraindicated per the package insert or in the investigators judgment will be excluded. Individuals on concomitant drugs which are not contraindicated but known to elevate blood levels SIGNIFICANTLY OR THOSE WITH MILD AEs (E.G. MILD DIARHEA) WILL receive qd dosing BASED ON CLINICIAN JUDGMENT. Consent, demographics, history, list of current medications, clinical and safety assessments, MMSE and blood tests (CBC, CMP, TSH, B-12 and Folic acid) will be performed at the Screening Visit. Medical history, physical exam, serum neuronal biomarkers and cytokines, serum ammonia level, Adverse Events and cognitive testing (ADAS-Cog-11) will be performed at the Baseline Visit. A stool sample collection kit will also be given to the subject and caregiver at the Baseline Visit, with instructions for use and how to get the sample back to the research coordinator. The stool sample will be obtained prior the subject taking the study drug. Medical history, physical exam, serum neuronal biomarkers and cytokines, serum ammonia level, Adverse Events and cognitive testing (ADAS-Cog-11) will be performed at the 3 month endpoint visit. A stool sample collection kit will also be given to the subject and caregiver at the baseline visit and 3 month Visit with instructions for use and how to get the sample back to the research coordinator. Interim safety checks will occur via phone calls one week after baseline and then every 2 weeks until the 3 month visit, which will then be followed by a 5 month phone call. Caregivers will be instructed to call the research coordinator or the PI ([name] after business hours or on weekends) if any change in stool is noticed at any time during the study. Unscheduled visit/labs may occur if warranted for safety based on clinical judgment. Because of a small risk of developing *C. difficile* up to 2 months following the last administration of rifaximin, the subjects will be followed for an additional 2 months after the 3 month treatment ends. Subjects who terminate early will receive the 3 month assessment at the time of termination.

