On no AD therapies or on stable (2 months) concurrent AD therapies

Exclusion Criteria

Subjects who meet one or more of the following criteria will not be considered eligible to participate in the clinical study:

Past history of C diff infection

Individuals on concomitant drugs which are contraindicated per the package insert or in the investigators judgment will be excluded

Assessment, laboratory examination, physical examination or any other medical condition or circumstance making the volunteer unsuitable for participation in the study in the judgment of the study clinicians

Allergy to Rifaximin

Antibiotic use in the last 6 months

Hospitalization in the last 6 months

Are taking medications that interact with Rifaximin

Are taking Cyclosporine

Past or current history of bloody stools or C Diff infection

Elevated LFTs

Clinically significant abnormal hepatic or renal function

Uncorrected thyroid or B12 abnormalities

Participation in another investigational drug trial in the past 30 days

History of febrile illness within 5 days prior to the study period

Hyperammonemia caused by:

Valproic acid

Chemotherapy

Lung transplant

Bariatric surgery

Ureterosigmoidoscopy

Hyperalimentation

Urinary tract infection

Errors of metabolism

Urea cycle

Enzyme deficiencies

Organic acidemias

Fatty acid oxidation

Amino acid transport defects

Lifestyle Considerations

Participation in the study will not have any impact on subject lifestyle.

Screen Failures

Volunteers who are consented to participate in the clinical trial and who do not meet one or more criteria required for participation in the trial during the screening procedures will not be rescreened later.

Strategies for Recruitment and Retention

Subjects will be recruited from referrals and the community via advertisement.

The study will be posted on clinicaltrials.gov.

Subjects and caregivers will be compensated for participation in the study at \$50 each per clinic visit to cover travel and time.

All tests and drug will be provided at no cost.

We expect to recruit 1 subject per month.

Study Intervention

Study Intervention Description

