**Protocol Title: Pilot, single center, open, trial of rifaximin in
probable Alzheimer's Disease**

NCT Number: NCT03856359

Date: September 6, 2019

Scientific Rationale for Study Design

This is an open label pilot study designed to provide preliminary evidence on the clinical efficacy of rifaximin in improving cognition in AD patients. We will be looking for improvement in test scores, changes in serum levels of neuronal markers and cytokines and changes in gut microbiota following treatment. We will also be collecting data regarding the safety of long-term use of this non-absorbed antibiotic for this disease. This pilot may form the basis for a future larger randomized, double blind controlled study to further test this hypothesis.

Summary statistics will be compiled for mean/SD change from baseline to endpoint on all cognitive, biomarker and microbiome variables. Statistics for cognitive and plasma biomarker tests will be based on nominal p-value of 0.05 given this is a pilot study. We will also examine multiplicity adjusted p-values for correlations between change in cognitive and biomarker/microbiome variables.

Statistical analyses will combined subjects on QD and BID for analyses as this is a pilot study and both doses may impact gut flora. In posthoc analyses we will put dosing as a covariate to examine dose effects.

As such any improvement in cognitive test score and/or significant correlations between cognition and microbiota changes will be viewed as a positive outcome to inform the design of a future larger study.

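### Blood ammonia, one of the two mechanisms under test, is judged on a two-point change in 10 subjects, with neither meal state nor time of day fixed for the draws

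*Protocol*

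**What the plan says.** **Role of ammonia.** The protocol Synopsis lists serum ammonia as a secondary endpoint, and the Objectives and Endpoints table lists blood ammonia. The Background gives two routes by which rifaximin might help: lower blood ammonia, lower pro-inflammatory cytokines, or both. If patients improve, "we will analyze our data to see if their improvement correlates with a lower blood ammonia level" is one of the planned analyses. The Ammonia Neurotoxicity subsection describes the gut as a major source of ammonia reaching the brain, through bacterial fermentation of protein. It also cites one study that found "significantly elevated post prandial blood ammonia levels in AD patients" relative to controls of the same age.

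**Sampling.** Study Design, Overall Design says of the pre-treatment visit: "serum ammonia level, Adverse Events and cognitive testing (ADAS-Cog-11) will be performed at the Baseline Visit". The same measurements are repeated at the 3-month visit. For Screening it says "MMSE and blood tests (CBC, CMP, TSH, B-12 and Folic acid) will be performed at the Screening Visit"; ammonia is not in that list. Neither document states a meal or time-of-day condition for any ammonia draw.

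**Visit schedule.** The table under Study Assessment and Procedures marks venipuncture and blood tests at Screening, Week 12 and Early Termination. It marks neither at Baseline, the visit at which study drug is dispensed.

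**Analysis.** The SAP says "Summary statistics will be compiled for mean/SD change from baseline to endpoint on all cognitive, biomarker and microbiome variables" and "Statistics for cognitive and plasma biomarker tests will be based on nominal p-value of 0.05 given this is a pilot study". It adds multiplicity-adjusted p-values for correlations between cognitive and biomarker change. The sample size is given as "we will consent up to 25 subjects in order to treat 10 eligible subjects with probable mild to moderate AD", with no power statement, effect size or SD.

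**The concern.** A change score built from one value before treatment and one after carries the sampling noise of both. With 10 subjects and no replicate draws there is little averaging to absorb it. On the protocol's own account of where ammonia comes from, recent food intake is a plausible influence on the measured level. A subject could be fed at one visit and fasting at the other, and the difference would enter the change score as if it were biology.

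Two planned results would suffer: the mean change in ammonia, and its correlation with cognitive change, which is how the protocol means to link improvement to this mechanism. A null ammonia result could then reflect sampling conditions as easily as absence of effect. If meal and draw times are not recorded, no later model can separate the two.

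**Working it through.** **No plan figure to reproduce.** The documents give N = 10 without power or SD, and no mean, SD or within-person variation for ammonia. What follows is an illustration under stated assumptions.

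**Inputs from the documents**
- n = 10 treated (Overall Design).
- Nominal alpha 0.05 (SAP).

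**Assumptions**
- The test is a two-sided paired t-test; the SAP names neither test nor sidedness. Ammonia is taken to fall under the SAP's biomarker tests.
- Meal-related variance equals k times the remaining variance of the change and is unrelated to everything else. The documents give no value for k; I use k = 0 to 1.
- A true correlation of 0.80 between ammonia change and cognitive change, chosen only to show the attenuation.

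**Mean change**
1. Power = P(|T| > t(0.975, 9)), where T is noncentral t with 9 df and noncentrality d × √10.
2. Solving for 80% power gives d = 0.996, about 1.00 SD of change.
3. Meal noise multiplies the SD by √(1 + k), so the detectable change becomes 0.996 × √(1 + k), in units of the SD without meal noise. For k = 0.5 this is 0.996 × 1.225 = 1.22; for k = 1 it is 0.996 × 1.414 = 1.41.
4. Power for the same true change uses d = 0.996 / √(1 + k).

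**Correlation**
1. Critical |r| at n = 10, unadjusted: t / √(8 + t²) with t = t(0.975, 8), which is 0.632.
2. Expected correlation after attenuation: 0.80 / √(1 + k).
3. Power by simulation, 100,000 bivariate normal samples of 10.

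| k (assumed) | Detectable change, SD | Power for a change of 0.996 SD | n for 80% power | Expected r (true 0.80) | Power for r |
|---|---|---|---|---|---|
| 0 | 1.00 | 80% | 10 | 0.80 | 87% |
| 0.25 | 1.11 | 71% | 12 | 0.72 | 71% |
| 0.5 | 1.22 | 63% | 14 | 0.65 | 58% |
| 1 | 1.41 | 51% | 18 | 0.57 | 43% |

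At k = 1 the expected correlation lies below the critical value, before any multiplicity adjustment.

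**Text against schedule.** Overall Design places the first ammonia measurement at Baseline. The schedule marks no venipuncture and no blood tests in that column, although vitals, stool sample and ADAS-Cog are marked there. If the schedule were followed and the Screening panel stayed as listed, there would be no pre-treatment ammonia value, and the change could not be computed at all.

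**The case against.** The strongest reply is that the effect of meals is inferred. The protocol reports one difference between AD patients and controls in post-prandial levels. It does not say that fasting levels were alike, or how far ammonia varies within a person. It also cites arteriovenous sampling in AD patients with normal ammonia, which is not described as post-prandial. The variance share k is assumed, zero cannot be ruled out, and a detectable change of about 1 SD is true of any paired test with n = 10. Ammonia is one of many secondary endpoints in a pilot, and the SAP's definition of a positive outcome rests on cognition and on its correlation with microbiota, not on ammonia.

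All of this stands, and it limits the weight of the point. It does not remove the omission: the sampling conditions are open, the protocol's own reasoning makes them relevant, and the gap can be closed only prospectively.

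A reader might go further and infer that the exclusion headed "Hyperammonemia caused by" cannot operate before dosing, so that excluded subjects would already be on drug and in the analysis. The documents do not show that. The criterion is a list of causes with no ammonia cut-off. Several, such as valproic acid, chemotherapy, lung transplant and bariatric surgery, can be identified from the history and medications collected at Screening. Overall Design has subjects evaluated for contraindications before drug is given. It also requires a stool sample, collected with a take-home kit, before the first dose, so a Baseline ammonia result could be available by then. At most, no ammonia value is required to be reviewed before dosing.

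Nor does drawing ammonia at the dispensing visit add noise in itself. A pre-dose sample there is a valid baseline.

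**Conclusion.** The point holds as a cheap improvement. A mechanistic secondary endpoint rests on two single draws per subject in 10 subjects, with meal state and time of day left open, in a protocol that itself treats the gut as a major ammonia source.

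The direction of the effect is sound: more variance in the change and a weaker correlation with cognition. Its size is not known from the documents. If meal timing adds 0 to 100% to the variance of the change, the detectable change moves from 1.00 to at most 1.41 SD, and power for the same true change from 80% to 51%. Those figures depend on the assumed range, on independent meal noise and on a two-sided paired t-test.

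The disagreement between Overall Design and the visit schedule could cost more than the noise, because it leaves unclear whether a pre-treatment ammonia value will exist. The claim that the hyperammonemia exclusion fails before dosing is not supported and forms no part of this conclusion.

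**What to change.** - Add one sentence to Overall Design: both ammonia samples are taken at the same stated interval from a meal and at the same time of day.
- Add two case report form fields per draw: clock time of the draw and time since the last meal.
- Reconcile Overall Design with the visit schedule so that both name the same pre-treatment visit for the ammonia draw and a pre-treatment value is certain.

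The cost is a few lines of protocol text, two form fields and tighter visit scheduling for subjects and caregivers. Standardizing the draws Overall Design already describes adds no assay. Recording the times is worth doing even where the schedule slips, because it leaves a basis for a sensitivity analysis.

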**Protocol Title: Pilot, single center, open, trial of
rifaximin in probable Alzheimer's Disease**

NCT Number: NCT03856359

Date: September 6, 2019

Synopsis

Title:	Pilot, single center, open, trial of rifaximin in probable Alzheimer's Disease" version date Sept. 6, 2019
Study Description:	Pilot trial to examine the relationship between rifaximin therapy and change in cognition, serum neuronal markers, ammonia levels and gut microbiota in patients with mild to moderate Probable Alzheimer's Disease.
Objectives:	
Primary Objective: To test if rifaximin treatment in subjects with AD is correlated with improvement in the ADAS-Cog.
 
Secondary Objective: To test if rifaximin treatment is associated with changes in serum amyloid-beta 42, total-tau, Neurofilament light protein markers, serum pro-inflammatory markers, ammonia levels and gut microbiota in AD subjects.

Endpoints:	
Primary Endpoints:
 
Cognitive domain – Alzheimer's Disease Assessment Scale-Cognitive (ADAS-Cog)

Endpoints:	
Primary Safety Endpoints will be Adverse Events
 
Secondary Endpoints:
 
Serum neuronal markers:
 
Neurofilament light (NF-L)Total TauAmyloid-beta 42 
Serum pro-inflammatory markers:
 
Interleukin (IL) 1 betaIL 2IL 4IL 5IL 6IL 8IL 10IL 13Tumor necrosis factor – alpha 
Gut microbiota
 
Serum Ammonia

Study Population:	Mild to moderate severity of Probable Alzheimer's Disease

Phase:	Pilot trial - 2a
Description of senior care facilities Sites/Facilities Enrolling Participants:	Single Site. Duke University Health System and affiliated
Description of Study Intervention:	Subjects will be treated with rifaximin (Xifaxan, Salix Pharmaceuticals, Bridgewater, NJ) 550 mg Orally twice a day for 12 weeks
Study Duration:	Up to 24 months (for recruitment, treatment, data analyses)
Participant Duration:	3 months treatment plus 2 month follow up

Introduction

There is an urgent need to develop novel therapies for Alzheimer's disease (AD). 10% of persons over age 65 and up to 50% over age 85 have dementia, with over 30 million people affected worldwide. The Food and Drug Administration (FDA) has approved cholinesterase inhibitors (Aricept, Exelon, Razadyne), memantine (Namenda), and a drug combining a cholinesterase inhibitor and memantine (Namzaric) to treat the cognitive symptoms of AD. These medications cannot cure AD or stop it from progressing.

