Rifaximin (Xifaxan, Salix Pharmaceuticals, Bridgewater, N.J.) (See Package Insert) is a drug that is approved by the FDA for use in humans for the treatment of Hepatic Encephalopathy, Traveler's Diarrhea and Irritable Bowel Syndrome. It is commercially available. It will be used in accordance with approved labeling as pertains to dosage and administration for Hepatic Encephalopathy, contraindications and warnings. However, it will be used investigational in this trial as rifaximin is not FDA approved for the treatment of Alzheimer's Disease.

Safety, Adverse Effects reporting and Management

The AE monitoring schedule is described in the protocol. The drug will be discontinued immediately if there are emergent signs of C.Difficile (e.g. patient has watery diarrhea for longer than 24 hours, fever, abdominal pain or possible bloody stools). All AEs will be assessed by a study physician and referred for appropriate treatment. The study drug may be discontinued at any time per the study physician judgment for safety. All SAEs will be reported to the IRB within 24 hours of becoming aware of the event.

Dosing and Administration

The drug will be administered orally, under supervision of the caregiver, 550 mg twice a day, for 3 months.

Drug Acquisition and Accountability

The drug, rifaximin, will be provided by the study and acquired from the manufacturer. Compliance will be monitored at phone calls and accountability through pill counts at the endpoint study visit.

Formulation, Packaging, Appearance and Labeling

Rifaximin will be packaged in bottles of 100 tablets of 550 mg. The product will be dispensed under the supervision of the study clinician.

Product Storage and Stability

Rifaximin will be stored in the clinical study office in a double locked facility in conditions suitable for its stability.

Preparation

No special measures are required to prepare the drug for oral administration.

Measures to Minimize Bias: Randomization and Blinding

This is an open label pilot study. Objective tests and biomarkers are used to minimize bias.

Study Intervention Compliance

The subject's caregiver will be asked to keep a log of rifaximin dosage and date and time of administration. This will insure compliance and adherence to the study protocol. The compliance log and pill count will be reviewed during the endpoint visit.

Concomitant Therapy

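### With the ADAS-Cog-11 given only at Baseline and Week 12 in one uncontrolled arm, any retest gain is part of the primary mean change and cannot be separated from drug effect; the net bias is unknown.

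*Protocol*

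**What the plan says.** The primary objective in the Protocol Synopsis is "To test if rifaximin treatment in subjects with AD is correlated with improvement in the ADAS-Cog". Under Study Design, Overall Design, "The study is single site and non-randomized", and the plan is that "we will consent up to 25 subjects in order to treat 10 eligible subjects with probable mild to moderate AD".

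The same section sets out the cognitive testing. At the first visit, "MMSE and blood tests (CBC, CMP, TSH, B-12 and Folic acid) will be performed at the Screening Visit"; the ADAS-Cog is not listed there. Then "cognitive testing (ADAS-Cog-11) will be performed at the Baseline Visit", and "cognitive testing (ADAS-Cog-11) will be performed at the 3 month endpoint visit". Subjects who stop early have the 3-month assessments when they stop. The schedule table under Study Assessment and Procedures agrees: the ADAS-Cog-11 row is marked at Baseline, Week 12 and early termination, and not at Screening.

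The Protocol section on randomization and blinding offers one safeguard: "Objective tests and biomarkers are used to minimize bias". Neither document describes a practice session, a repeated baseline, alternate forms, an external comparator or an expected-change benchmark.

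The SAP summarises change from baseline by its mean and SD and applies a nominal 0.05 level to the cognitive tests. It then says that "any improvement in cognitive test score and/or significant correlations between cognition and microbiota changes will be viewed as a positive outcome", for the purpose of informing the design of a larger study.

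**The concern.** Each subject's primary outcome is the difference between a first and a second in-study sitting of the same test. If familiarity with the tasks, the word lists, the rater or the setting helps the second sitting, that help is part of the change score. A concurrent control would carry the same help and cancel it, but this trial has none. Objective scoring does not address the problem, because a correctly scored second attempt can still be better for reasons unrelated to the drug.

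The SAP's reading of the result raises the stakes. A rule that counts any improvement as positive has no threshold, so even a small non-drug shift can change the conclusion. The Protocol says the pilot may form the basis of a randomized trial, so a shifted mean change could carry into that trial's planning. Early terminators add a further difficulty, since their retest interval may be shorter than 12 weeks.

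**Working it through.** The plan states no effect size, SD, power or derivation for its sample size, so there is no figure of its own to reproduce. The check has two parts.

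**1. Is there any ADAS-Cog-11 before Baseline, or anything else that would isolate a retest shift?** The Overall Design text and the schedule table both say no. The Screening MMSE gives some exposure to cognitive testing, but it is not an ADAS-Cog administration.

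**2. How much could a non-drug change matter?**

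From the documents: n = 10 treated; one arm; change from baseline; nominal level 0.05.

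Assumptions, not in the documents:
- the true drug effect is 0;
- the net non-drug change g (retest gain minus untreated decline, positive meaning improvement) is -1 to +2 points;
- the SD of change is 4 to 6 points;
- the test is a two-sided paired t-test, since the SAP names neither the test nor its sidedness;
- any improvement means an improved group mean.

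Formulas:
- ncp = g × √10 / SD
- P(mean improves) = Φ(ncp)
- P(nominally significant improvement) = upper tail, beyond 2.262, of the noncentral t with 9 degrees of freedom and noncentrality ncp

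Example with g = 1 and SD = 5: ncp = 1 × 3.162 / 5 = 0.632. P(mean improves) = Φ(0.632) = 73.6%, and P(significant improvement) = 8.2%.

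Each cell gives P(mean improves) / P(nominally significant improvement):

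| Net non-drug change g | SD 4 | SD 5 | SD 6 |
|---|---|---|---|
| -1 | 21% / 0.4% | 26% / 0.6% | 30% / 0.7% |
| 0 | 50% / 2.5% | 50% / 2.5% | 50% / 2.5% |
| +0.5 | 65% / 5.4% | 62% / 4.7% | 60% / 4.2% |
| +1 | 79% / 10.6% | 74% / 8.2% | 70% / 6.9% |
| +2 | 94% / 29.3% | 90% / 20.4% | 85% / 15.5% |

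Over the whole grid, the first probability runs from 21% to 94% and the second from 0.4% to 29%.

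**Could a Screening ADAS-Cog-11 measure the bias?** With n = 10, the 95% half-width for a mean Screening-to-Baseline change is 2.262 × SD / √10. Borrowing the same SDs, that is 2.9 points at SD 4 and 3.6 at SD 5, wider than the largest gain considered here (2 points). It would also be a first-to-second exposure over an interval the Protocol does not state, whereas Baseline to Week 12 would then be second-to-third over 12 weeks.

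**Does the order of parallel lists matter?** Suppose list B is d points easier than list A. If all subjects take A then B, the mean change shifts by d, indistinguishable from drug effect. With five subjects in each order, the shift is (5 × d − 5 × d) / 10 = 0, and the list difference shows up as extra variance instead.

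**The case against.** The strongest reply is that no passage shows that a retest gain exists in patients with MMSE 10-22 after 12 weeks, let alone how large it is. Decline also pulls the other way: the Protocol's Introduction says that current medicines do not stop progression. If gain and decline cancel, the figures return to 50% and 2.5%; if decline wins by a point, they fall to 21-30% and 0.4-0.7%. This stands. A reader might infer that the design favours rifaximin on balance. The documents do not support that, because they give neither quantity. What remains is that an unmeasured offset is not a control.

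A second reply is that this is a declared open-label pilot, offered as preliminary evidence ahead of a possible randomized trial. That also stands: it limits the consequence and is why I do not ask for a control arm. The any-improvement rule is met half the time with no effect of any kind, so part of the weakness lies in that rule and not in retesting. Pilot status is still no reason to leave out a cheap protection.

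Third, silence is not proof. Word lists and rater procedures may be set out in a rating manual that is not among these documents. A reader might infer that the same list is reused or that the Week 12 rater sees the Baseline score. Neither is stated; the Protocol simply does not exclude either.

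**Conclusion.** The point holds in conditional form. Any retest gain on the ADAS-Cog-11 is counted in the primary mean change, and nothing in the plan lets it be separated from drug effect. Its size is unknown and untreated decline opposes it, so neither the sign nor the size of the net bias can be given. The range of 21-94% for an improved mean, and 0.4-29% for a nominally significant one, rests on my assumed net changes of -1 to +2 points, SDs of 4 to 6, a two-sided paired t-test and an inert drug. It shows how sensitive the result is and does not predict bias in either direction.

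A reader might also infer that an extra Screening test would reveal the bias in the Week 12 result. It would not: it covers a different exposure step and interval, and is too imprecise at n = 10. Only a concurrent control would remove retest gain together with the other effects of time. The changes proposed are worth making because they reduce part of the problem at visits that already exist.

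**What to change.** **Protocol, Overall Design and the section on minimizing bias.**
- Use parallel ADAS-Cog word lists at Baseline and Week 12 (or early termination), with the order counterbalanced: half the subjects take A then B, half B then A. A single order for everyone would confound list difficulty with treatment.
- Have the Week 12 rater score without access to the Baseline sheet.

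Both fit existing visits and need no extra staff. The downside is a little added variance from differences between lists. Parallel lists reduce memory for the words but not familiarity with the other tasks or the setting.

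**Optional.** Give a practice ADAS-Cog-11 at Screening to subjects whose MMSE qualifies, only to reduce first-exposure effects. It should not serve as the baseline or be reported as an estimate of the bias in the Week 12 change. The cost is one more test session, including for some subjects who later fail screening on other criteria.

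**SAP.** Replace the rule that any improvement is a positive outcome with the mean ADAS-Cog-11 change and its 95% CI. State beside it that retest gain and natural decline are not separated from drug effect. This costs nothing beyond the wording.
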